6.3.1 Baseline Data

Participants will be matched on demographic data.

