3.1 General Design

This study uses neurofeedback to target neural mechanisms underlying attentional bias in participants with major depressive disorder (MDD), with the goal of evaluating whether this intervention can be used to reduce the negative attentional bias.

Following random assignment, participants will begin the protocol with either active neurofeedback or sham (yoked) neurofeedback.

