3.2 Allocation to Interventional Group

Participants will be randomly assigned to treatment with active neurofeedback or sham. At the end of the initial assessment, a computer-generated random number list will be used to allocate participants to the two treatment conditions.

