6.2 Statistical Methods

Statistical analysis will be performed using the R statistical environment assuming 5% type I error rates. Linear mixed effects regression modeling (using the lme4 R package) will be used to assess evidence of reduced neural perseveration and reduced MADRS over time in the active neurofeedback group. Two-sample t-tests will be used to compare differences in neural perseveration and MADRS scores between the active neurofeedback and sham (yoked) neurofeedback groups after each additional session of treatment in order to establish the lowest dose of training necessary to significantly reduce neural perseveration. We will utilize multiple linear regression to assess the relationship between reduced perseveration and the reduction of MADRS scores in the active neurofeedback group while accounting for various confounds.

6.3 Control of Bias and Confounding (if applicable, typically observational study or if randomization is not taking place)

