6.3.2 Analysis of Primary Outcome of Interest

We will use a two-sample t-test comparison of active neurofeedback vs sham to determine the effect on MADRS scores.

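### Section 6.3.1 promises demographic matching that neither the allocation described in 3.2 nor the unadjusted between-arm t-tests provide

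*Combined protocol and SAP*

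**What the plan says.** Section 6.3.1, on baseline data, reads in full: "Participants will be matched on demographic data". It gives no variables, ratio, tolerance or procedure.

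Section 3.2 places allocation "At the end of the initial assessment" and says that "a computer-generated random number list will be used to allocate participants to the two treatment conditions". It does not mention stratification, blocking, minimisation or pairing.

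On analysis, 6.3.2 states: "We will use a two-sample t-test comparison of active neurofeedback vs sham to determine the effect on MADRS scores". Section 6.2 uses the same kind of test after each session: "Two-sample t-tests will be used to compare differences in neural perseveration and MADRS scores between the active neurofeedback and sham (yoked) neurofeedback groups". The two richer models in 6.2 are confined to one arm. The mixed model "will be used to assess evidence of reduced neural perseveration and reduced MADRS over time in the active neurofeedback group", and the multiple regression concerns "the reduction of MADRS scores in the active neurofeedback group while accounting for various confounds", with the confounds not named.

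Section 3.1 says that "participants will begin the protocol with either active neurofeedback or sham (yoked) neurofeedback". Neither 3.1 nor 6.2 says whose feedback a yoked sham participant receives, or how many sham participants share one source.

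**The concern.** Matching and allocation from a plain random list are different procedures. Staff who follow 3.2 as described will not have matched anyone. Staff who try to honour 6.3.1 have no procedure to follow and would have to depart from the list. The team needs to know which sentence governs before the first participant is allocated.

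Nothing elsewhere fills the gap. Section 6.3.1 is the only statement about balancing baseline characteristics, and no between-arm analysis adjusts for demographics or baseline severity. In a trial of 60 and then 80 participants, pre-training MADRS is likely to be among the stronger predictors of later MADRS. It is already collected, and the primary comparison does not use it. What is at stake is clarity of conduct and precision, not validity.

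**Working it through.** **The passages side by side.** Section 6.3.1 requires matching on unnamed demographics. Section 3.2 contains no step that uses a demographic variable. Section 6.3.2 fits no demographic or baseline term. The section 5 visit table puts the demographics survey and the MADRS at the pre-training visit, before allocation, so the information needed for balancing exists when it is needed.

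**The plan's own figures.** No figure in the plan depends on the matching. The attrition arithmetic reproduces: 27/0.9 = 30 and 36/0.9 = 40 per arm. The two-sample detectable effects in 6.1 (0.86 and 0.74) come out at 0.78 and 0.67 at two-sided 5% and 80% power. That is a separate matter and nothing below uses it.

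**1. Balance without stratification.** For a standardised baseline variable with n per arm, the probability of a between-arm difference above 0.3 SD is 2[1 − Φ(0.3/√(2/n))].
- n = 30: 0.3/0.258 = 1.16, giving 24.5%.
- n = 40: 0.3/0.224 = 1.34, giving 18.0%.

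This is ordinary chance imbalance. It shows only that a plain list does not deliver what 6.3.1 promises.

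**2. Arm sizes if the list is unrestricted** (a reading of silence in 3.2). From Binomial(N, 0.5):
- N = 60: exactly 30:30 has probability 10.3%, and a difference of 8 or more 36.6%.
- N = 80: 8.9% and 43.4%.

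The effect on precision is slight. For 26:34 the standard error ratio is √[(1/26 + 1/34)/(2/30)] = 1.009. For 36:44 it is √[(1/36 + 1/44)/(2/40)] = 1.005.

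**3. Precision forgone.** Let r be the correlation between pre-training and post-treatment MADRS, assumed 0.3 to 0.7. Section 6.3.2 does not say whether the t-test uses post-treatment or change scores, so both are shown. The ANCOVA standard error is √(1 − r²) times that of a t-test on post-treatment scores. With equal variances it is √[(1 + r)/2] times that of a t-test on change scores.

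| r (assumed) | Reduction vs post-treatment scores | Reduction vs change scores |
|---|---|---|
| 0.3 | 1 − √0.91 = 5% | 1 − √0.65 = 19% |
| 0.5 | 1 − √0.75 = 13% | 1 − √0.75 = 13% |
| 0.7 | 1 − √0.51 = 29% | 1 − √0.85 = 8% |

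The MADRS entry minimum of 16 truncates the baseline range, which tends to hold r down. The upper end should not be taken for granted.

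**4. Yoking (conditional).** Suppose 1:1 active-sham pairs with within-pair correlation ρ, assumed 0.1 to 0.3. The true variance of the difference is (1 − ρ) times the unpaired value, so the unpaired standard error is too wide by 1/√(1 − ρ) − 1, or 5% to 20%. The actual two-sided error is 2[1 − Φ(1.96/√(1 − ρ))], or 3.9% to 1.9%.

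Suppose instead that each donor serves k sham participants who share correlation ρ with one another.
- Donors outside the trial: the variance factor is [2 + (k − 1)ρ]/2. For k = 6 the error is 8.0% to 13.8%; for k = 3 it is 6.2% to 8.6%.
- Donors in the active arm, with the same ρ to their recipients: the factor is [2 + (k − 3)ρ]/2. For k = 6 the error is 6.8% to 10.4%; for k = 3 it stays at 5%.

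Both k and ρ are assumptions. The documents supply neither.

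**The case against.** **The list could be balanced.** Section 3.2 does not say how the list is built. A stratified or minimised list could balance a few named factors and remain random. This stands: a reader might infer that matching and randomisation are incompatible in principle, or that allocation is compromised and foreseeable, but the documents show only that no balancing method is described.

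**The sentence may be template residue.** The heading of 6.3 marks the section as typically meant for observational or non-randomised studies, so the sentence may be a loose reference to comparable groups. That is plausible, and it supports deletion. It does not make the sentence harmless while it remains in the plan.

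**Randomisation already controls baseline differences.** It does. Chance imbalance does not bias the t-test or alter its 5% error rate, and the 24.5% and 18.0% figures would apply to any unstratified covariate. The arm-size probabilities look striking but cost under 1% in standard error. Both belong in the background.

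**No pairs are shown to exist.** A reader might infer from the words for matching and yoking that the data are paired and the unpaired test therefore wrong. The documents do not support that. Donors may come from outside the trial, replayed feedback need not correlate MADRS outcomes, and positive 1:1 pairing would only make the test conservative. This part remains conditional.

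**Conclusion.** The conflict between 6.3.1 and 3.2 is real and rests on the text alone, with no assumption. The balance that 6.3.1 states is not secured by the allocation as described and is not handled in any between-arm analysis. The consequence is an instruction that cannot be carried out alongside 3.2 as written, and lost precision: about 5% to 29% of the standard error against post-treatment scores, or 19% to 8% against change scores, over r = 0.3 to 0.7 (assumed). The randomised comparison stays unbiased, and no stated sample size changes.

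The yoking point is subsidiary. The scheme is undescribed, so even the direction of any error in the t-test is unknown: conservative with positively correlated 1:1 pairs, possibly anti-conservative if donors are reused.

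**What to change.** 1. Delete the matching sentence in 6.3.1.
2. In 3.2, state that allocation uses a concealed list in permuted blocks of varying size, stratified by a small number of factors known before allocation, for example sex and pre-training MADRS category. The factors are the sponsor's choice; with 60 and 80 participants they should be few.
3. In 6.3.2, replace the t-test with a linear model (ANCOVA) of MADRS on arm, adjusted for pre-training MADRS and the stratification factors. The pre-training score is the right covariate because it precedes allocation.
4. Describe the yoking and record the donor of each sham run. If donors are trial participants or are reused, add a pair or donor effect as a sensitivity analysis.

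The cost is a little more randomisation set-up, a few lines of analysis code and one stored donor identifier per sham run. No new assessment is needed. The donor record should start with the first sham run, because it may not be recoverable later.

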6.3.2 Analysis of Primary Outcome of Interest

We will use a two-sample t-test comparison of active neurofeedback vs sham to determine the effect on MADRS scores.

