3.4 Study Endpoints

3.4.1 Primary Study Endpoint

Our primary aim to test the efficacy of the closed loop real time fMRI neurofeedback: does this neurofeedback that specifically targets our hypothesized attentional mechanism of depression (i.e., neural perseveration of negative states) lead to reduced depression severity? The primary endpoint would then be a change in negative attention bias following training visits. Phase R61 will focus on this negative attention bias, and Phase R33 will focus on change in depressive symptom severity.

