4.3 Inclusion Criteria

- gender, inclusive
- adult aged 18 – 65

CONFIDENTIAL

- meets Diagnostic and Statistical Manual of Mental Disorders (DSM-5) criteria for MDD according to the Clinician-Administered MDD Scale for DSM-5 (unipolar depression or bipolar II depressed)
- scores at least a minimum score of 16 on Montgomery Asberg Depression Rating Scale (MADRS)
- normal cognition
- participants must be able to read and understand English
- participants must be able to provide consent

4.4 *Exclusion Criteria*

- pregnancy (female participants)
- outside age range
- MRI contraindications (medical implant, claustrophobia, etc.)
- use of psychoactive medication (including antidepressants) or currently in therapy
- neurological disorder or any condition that in the view of the PI could impact brain data, cause depression, require medication that could cause depressive symptoms, or otherwise result in participant being unfit for study (for example, co-morbid psychotic, neurological disorders, developmentally or cognitively disabled/impaired, active alcohol or drug abuse/dependence within the past 6 months).
- non-English speaking
- non-correctable vision loss
- refusal to provide informed consent
- representing an active suicide risk

4.5 *Subject Recruitment*

All participants will be recruited through the University of Pennsylvania and surrounding community. For both phases, recruitment will occur through the Center for Neuromodulation in Depression and Stress (CNDS) directed by the PI. All subjects will express interest by initiating contact with the research staff for a center wide phone screening or self-screening procedure. All subjects fitting inclusion criteria will be approached by study staff to continue in the study. This study will also be advertised on online sources such as Facebook. Study coordinators in the present study will use the results in REDCap as a source of recruitment, at which point those subjects will undergo the full phone-screen. This phone screen will also be collected and stored in REDCap. In addition to recruiting from the CNDS, we will recruit from the larger Philadelphia community through targeted advertisements and referral streams at the University of Philadelphia. This includes both print and online sources. All recruitment materials, including but not limited to flyers, brochures, referral letters, online postings, and email templates will be IRB-approved before distribution of any of these material.

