- For a one-sample t-test with a two-sided alternative and type I error rate of 5%, 36 participants per arm will yield 80% power for a Cohens $d = 0.53$ or larger, which is sufficient to detect the effect size of 0.93 Visit 1 to post-treatment MADRS score decrease in the pilot data (**Hypothesis 1**). For a two-sample t-test with a two-sided alternative and type I error rate of 5%, 36 participants will yield 80% power for a Cohens $d = 0.74$ or larger. **Hypothesis 2** will utilize Pearson correlation between change in MADRS and change in negative attention scores. If nonlinearity is detected, we will employ a Spearman correlation analysis. A sample size of n=36 corresponds to 80% power to detect a significant (at 5% alpha level) correlation as low as $r=0.45$, which is sufficient to detect the effect size of $r=0.48$ found in the pilot data (**Figure 1**). **Hypothesis 3** will use a two-sample t-test comparing real vs sham NF. Pilot study data indicated a change in MADRS from baseline to 3 month follow-up corresponding to Cohen's $d=0.95$. A two-sample t-test, with 36 per group, at 5% significance level, gives 80% power to detect $d=0.74$ or larger.

CONFIDENTIAL

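### The between-arm MADRS tests are t-tests with no baseline covariate, although a pre-randomisation MADRS is available for every participant; this gives up precision, not validity

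*Combined protocol and SAP*

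**What the plan says.** Section 6.3.2 gives the primary analysis in one sentence: "We will use a two-sample t-test comparison of active neurofeedback vs sham to determine the effect on MADRS scores". In section 6.1, Hypothesis 3 "will use a two-sample t-test comparing real vs sham NF". Neither mentions a baseline covariate. Section 6.3.2 also leaves open the phase, the visit, and whether the score is the later value or a change.

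A change score is implied in two places. Section 3.4.1 says "Phase R33 will focus on change in depressive symptom severity". Section 6.1 cites pilot effects described as "Visit 1 to post-treatment MADRS score decrease in the pilot data" (Hypothesis 1) and "change in MADRS from baseline to 3 month follow-up" (Hypothesis 3). Neither place defines change as the variable tested between arms. Hypothesis 2 does use a change in MADRS, but for a correlation.

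No other section fills the gap:

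- The mixed model in 6.2 assesses "reduced MADRS over time in the active neurofeedback group". The multiple regression there is likewise confined to the active group.
- The between-arm comparisons in 6.2, made after each session, are again two-sample t-tests.
- Section 6.3.1, on baseline data, mentions only demographic matching.

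A suitable covariate already exists. Section 4.3 requires a MADRS of at least 16 for entry, section 5.1 has it taken at the pre-training visit, and section 3.2 states: "At the end of the initial assessment, a computer-generated random number list will be used to allocate participants to the two treatment conditions".

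**The concern.** Section 5.1 calls MADRS the primary outcome measure, and the R33 phase exists to compare arms on depression outcome. Baseline severity usually predicts later severity. A comparison that ignores it leaves explainable variance in the error term and lets a chance difference at entry pass into the estimate. A change score uses baseline, but fixes its coefficient at 1 instead of estimating it, so it over-corrects whenever the true slope is below 1. Which t-test is the better one depends on a correlation that the team does not know beforehand, and 6.3.2 does not say which is meant. At stake is power in a comparison of 36 completers per arm, together with an open choice of score and visit that should be closed before R33 data are seen.

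**Working it through.** **Inputs from the documents.** 36 completers per arm, two-sided test, 80% power and detectable d = 0.74 (section 6.1); 5% type I error (6.1 and 6.2).

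**Assumed, because the documents do not give them.** The correlation rho between baseline and later MADRS: 0.3, 0.5, 0.7. The ratio k of baseline SD to later SD: 1, 0.85, 0.7. The entry floor of 16 restricts baseline only, so k may fall below 1. The effect d = 0.5 in later-score SD units, with the plan's 0.74 as a second case.

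**The plan's own figure.** Noncentral-t power with 36 per arm, two-sided 5%, gives a detectable d of 0.67 at 80% power, not 0.74; at d = 0.74 power is 87%. The stated 0.74 matches a two-sided alpha of 0.025. That alpha is inferred from the number and is not stated. The discrepancy is conservative and is a separate point. It is given here so that the figures below can be related to the plan.

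**Error variance, in units of the later-score variance.**

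- Later-score t-test: 1
- Change-score t-test: 1 + k² − 2·rho·k
- ANCOVA: 1 − rho²

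| | rho 0.3 | rho 0.5 | rho 0.7 |
|---|---|---|---|
| Later score | 1 | 1 | 1 |
| Change, k = 1 | 1.400 | 1.000 | 0.600 |
| Change, k = 0.85 | 1.2125 | 0.8725 | 0.5325 |
| Change, k = 0.7 | 1.070 | 0.790 | 0.510 |
| ANCOVA | 0.910 | 0.750 | 0.510 |

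Example: at k = 1 and rho = 0.3, change gives 1 + 1 − 0.6 = 1.400 and ANCOVA 1 − 0.09 = 0.910, a cut of 1 − 0.910/1.400 = 35%. At k = rho = 0.7 both give 0.510 and the cut is nil.

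**Cost of estimating the slope.** With 72 completers, ANCOVA has 69 degrees of freedom against 70, and its variance rises on average by 69/68 = 1.015, about 1.5%. The ANCOVA powers below include this.

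**Power.** The noncentrality is d / sqrt(variance × 2/36).

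| | d = 0.5: rho 0.3 / 0.5 / 0.7 | d = 0.74: rho 0.3 / 0.5 / 0.7 |
|---|---|---|
| Later score | 55 / 55 / 55% | 87 / 87 / 87% |
| Change, k = 1 | 42 / 55 / 77% | 74 / 87 / 98% |
| Change, k = 0.85 | 48 / 61 / 82% | 80 / 91 / 99% |
| Change, k = 0.7 | 53 / 65 / 83% | 85 / 94 / 99% |
| ANCOVA | 59 / 67 / 83% | 90 / 94 / 99% |

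At d = 0.5 the largest gain over change is 58.6 − 42.4 = 16.2 points (k = 1, rho = 0.3). The smallest is 82.8 − 83.4 = −0.6 (k = rho = 0.7). Over the later-score test, using 55.3% before rounding, the gains are 58.6 − 55.3 = 3.3, 66.9 − 55.3 = 11.6 and 82.8 − 55.3 = 27.5 points. At d = 0.74 the gain over change runs from 89.6 − 74.4 = 15.2 points to none (99.0 against 99.1).

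**Chance imbalance.** The SD of the baseline difference between arms is sqrt(2/36) = 0.236 baseline SD, so the probability of a difference above 0.25 SD in either direction is about 29%. A difference of that size moves a later-score estimate by 0.25 × rho = 0.08/0.13/0.18 SD. It moves a change estimate the opposite way by 0.25 × (k − rho): 0.18/0.13/0.08 SD at k = 1, and 0.10/0.05/0.00 SD at k = 0.7.

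**The case against.** The strongest reply is that the t-test is valid under randomisation, so this is a preference about efficiency. The first half stands. A reader might infer that the unadjusted comparison is biased or that the R33 result could not be trusted. The documents do not support that: allocation is random, and with complete data the t-test is unbiased over repeated randomisations.

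A second reply is that the text points to a change score, which already uses baseline. That also has force. If change is meant and k is well below 1, the gain is small: at d = 0.5 and k = 0.7 it is 6, 2 and −0.6 points. But change is never specified for this test, and its performance depends on an unknown correlation. ANCOVA does at least as well as either t-test apart from the slope cost.

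Third, the size rests on assumed values. The grid varies rho and k independently, although an entry floor that narrows the baseline distribution would also tend to lower rho. The gains over a later-score test at high rho are therefore the less certain ones.

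A reader might also infer from 6.1 that this trial's change score has two different starting points, Visit 1 and baseline. Those phrases describe pilot results. They do not define the variable to be tested here, and whether they mean different visits cannot be judged from the documents.

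**Conclusion.** The point holds as a loss of precision and of protection against chance imbalance; it is not an error of validity. Section 6.3.2 and Hypothesis 3 compare arms without the baseline covariate that every randomised participant should have, and no other section supplies an adjusted comparison. Under the assumed rho and k, ANCOVA gains at best about 16 points of power over a change score at d = 0.5 and about 15 at d = 0.74. At worst it loses about 0.6 points at d = 0.5 and nothing material at d = 0.74. The d = 0.74 case further assumes that the plan's figure is in later-score SD units, which the plan does not say. The change should be made because it costs almost nothing and settles the score and visit at the same time.

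**What to change.** In 6.3.2 and Hypothesis 3, state the phase and make the primary analysis an ANCOVA of the MADRS score at a named visit on arm, with the pre-training (pre-randomisation) MADRS as covariate. Report the adjusted active-minus-sham difference with its 95% confidence interval. Keep the two-sample t-test as a sensitivity analysis and say whether it uses the later score or a change from a named visit.

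Do not use the Training Visit 1 MADRS as the covariate unless the protocol states that it is taken before the first feedback. It follows allocation, and section 5.2.1 does not give its timing within the visit.

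Before the Hypothesis 3 visit is named, the follow-up passages must be reconciled: 6.1 cites a 3-month pilot figure, 4.1 and 5.2.4 describe one follow-up at 1 month, and sections 3 and 5 give two follow-ups. That is a separate point and does not affect the choice of model.

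The cost is SAP wording and one degree of freedom (about 1.5% of variance). No new visits, measurements or participants are needed. R33 runs only if R61 succeeds, so the text can be settled before R33 begins.

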6.3.3 Pharmacokinetic Analysis (only if applicable): N/A

6.3.4 Interim Analysis (only if applicable): N/A

7 Safety and Adverse Events

